9.2.8.2. Hematology for Complete Blood Count and Differential

Neutrophil-lymphocyte ratio (NLR) will be assessed, as well as other hematological biomarkers. NLR is an inflammatory marker that may serve as an independent risk factor for in-hospital mortality of patients with COVID-19. Assessment of NLR trends may therefore aid in identifying patients with COVID-19 who are at higher risk of complications (Liu, 2020) (Qin, 2020). Relationships will be evaluated between NLR and clinical outcomes in treatment versus placebo arms.

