5.7. Analysis of Safety Data

The analysis of safety data will be performed for cohort 1 in combined phases 1, 2 and 3, phase 2 cohorts 1A, 2 and 3, separately in the FAS population.

In this study, only targeted treatment-emergent adverse events will be recorded:

- All phases: Treatment-emergent adverse events of special interest (AESIs)
 - Grade ≥ 2 hypersensitivity
 - Grade ≥ 2 infusion-related reactions
- All phases: Treatment-emergent serious adverse events (SAEs)
- All phases: TEAEs (Grade 3 or Grade 4 only)

The safety analysis will be based on the reported SAEs and AESIs and other safety information (clinical laboratory evaluations and vital signs).

Thresholds for Potential Clinically Significant Values (PCSV) in laboratory variables and vital signs are defined in Section [10.3](#).

The summary of safety results will be presented for each treatment group.

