5.7.3. Analysis of Vital Signs

Vital signs (temperature, pulse, blood pressure, SpO₂, FiO₂, and respiration rate) will be summarized using descriptive statistics. Number and percentage of patients with a potentially clinically significant value (PCSV) at any post-randomization time point will be summarized.

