Hyponatremia:	$\leq 129 \text{ mmol/L}$ or $\leq \text{LLN}$ (if $\text{LLN} \leq 129 \text{ mmol/L}$) and baseline $> 129 \text{ mmol/L}$ or $> \text{LLN}$ (if $\text{LLN} \leq 129 \text{ mmol/L}$) $\geq 160 \text{ mmol/L}$ or $\geq \text{ULN}$ (if $\text{ULN} \geq 160 \text{ mmol/L}$) and baseline $< 160 \text{ mmol/L}$ or $< \text{ULN}$ (if $\text{ULN} \geq 160 \text{ mmol/L}$)	Two independent criteria
Hypernatremia:		

Parameter	PCSV	Comments
Potassium	<3 mmol/L or <LLN (if LLN≤3 mmol/L) and baseline ≥ 3 mmol/L or ≥LLN (if LLN≤3 mmol/L)	FDA Feb 2005.
Hypokalemia	≥5.5 mmol/L or ≥ULN (if ULN≥5.5 mmol/L) and baseline <5.5 mmol/L or <ULN (if ULN≥5.5 mmol/L)	Two independent criteria
Hyperkalemia		
Total Cholesterol	≥7.74 mmol/L or ≥ULN (if ULN≥7.74 mmol/L) and baseline < 7.74 mmol/L or <ULN (if ULN≥7.74 mmol/L)	Threshold for therapeutic intervention.
Triglycerides	≥4.6 mmol/L or ≥ULN (if ULN≥4.6 mmol/L) and baseline < 4.6 mmol/L or <ULN (if ULN≥4.6 mmol/L)	Threshold for therapeutic intervention.
Lipasemia	≥3 ULN and baseline < 3 ULN	
Amylasemia	≥3 ULN and baseline < 3 ULN	
Glucose		
Hypoglycaemia	≤3.9 mmol/L and <LLN and baseline >3.9 mmol/L or ≥ LLN ≥11.1 mmol/L (unfasted); ≥7 mmol/L (fasted) and baseline < 11.1 mmol/L (unfasted); <7 mmol/L (fasted)	ADA Jan 2008.
Hyperglycaemia		
HbA1c	>8% and baseline ≤ 8%	
Albumin	≤25 g/L or ≤LLN (if LLN≤25 g/L) and baseline >25 g/L or >LLN (if LLN≤25 g/L)	
CRP	>2 ULN or >10 mg/L (if ULN not provided) and baseline ≤2 ULN or ≤10 mg/L (if ULN not provided)	FDA Sept 2005.
Hematology		

Parameter	PCSV	Comments
WBC	$<3.0 \text{ Giga/L}$ or $<\text{LLN}$ (if $\text{LLN} \leq 3.0 \text{ Giga/L}$) and baseline $\geq 3.0 \text{ Giga/L}$ or $\geq \text{LLN}$ (if $\text{LLN} \leq 3.0 \text{ Giga/L}$) (Non-Black); $<2.0 \text{ Giga/L}$ or $<\text{LLN}$ (if $\text{LLN} \leq 2.0 \text{ Giga/L}$) and baseline $\geq 2.0 \text{ Giga/L}$ or $\geq \text{LLN}$ (if $\text{LLN} \leq 2.0 \text{ Giga/L}$) (Black)* $\geq 16.0 \text{ Giga/L}$ or $\geq \text{ULN}$ (if $\text{ULN} \geq 16.0 \text{ Giga/L}$) and baseline $< 16 \text{ Giga/L}$ or $<\text{ULN}$ (if $\text{ULN} \geq 16.0 \text{ Giga/L}$)	Increase in WBC: not relevant. *The default criteria. Summary by race (black and Non-black) are optional. To be interpreted only if no differential count available.

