Lymphocytes	$>4.0 \text{ Giga/L}$ or $>\text{ULN}$ (if $\text{ULN} \geq 4.0 \text{ Giga/L}$) and baseline $\leq 4.0 \text{ Giga/L}$ or $\leq \text{ULN}$ (if $\text{ULN} \geq 4.0 \text{ Giga/L}$)	
Neutrophils	$<1.5 \text{ Giga/L}$ or $<\text{LLN}$ (if $\text{LLN} \leq 1.5 \text{ Giga/L}$) for Non-Black or $<1.0 \text{ Giga/L}$ or $<\text{LLN}$ (if $\text{LLN} \leq 1.0 \text{ Giga/L}$) for Black and baseline $\geq 1.5 \text{ Giga/L}$ or $\geq \text{LLN}$ (if $\text{LLN} \leq 1.5 \text{ Giga/L}$) for Non-Black or $\geq 1.0 \text{ Giga/L}$ or $\geq \text{LLN}$ (if $\text{LLN} \leq 1.0 \text{ Giga/L}$) for Black* $<1.5 \text{ Giga/L}$ or $<\text{LLN}$ (if $\text{LLN} \leq 1.5 \text{ Giga/L}$) and baseline $\geq 1.5 \text{ Giga/L}$ or $\geq \text{LLN}$ (if $\text{LLN} \leq 1.5 \text{ Giga/L}$) (Non-Black); $<1.0 \text{ Giga/L}$ or $<\text{LLN}$ (if $\text{LLN} \leq 1.0 \text{ Giga/L}$) and baseline $\geq 1.0 \text{ Giga/L}$ or $\geq \text{LLN}$ (if $\text{LLN} \leq 1.0 \text{ Giga/L}$) (Black) $<0.5 \text{ Giga/L}$ regardless of baseline value or race	International Consensus meeting on drug-induced blood cytopenias, 1991. *The default criteria. By race (black and Non-black) are optional.
Monocytes	$>0.7 \text{ Giga/L}$ or $>\text{ULN}$ (if $\text{ULN} \geq 0.7 \text{ Giga/L}$) and baseline $\leq 0.7 \text{ Giga/L}$ or $\leq \text{ULN}$ (if $\text{ULN} \geq 0.7 \text{ Giga/L}$)	
Basophils	$>0.1 \text{ Giga/L}$ or $>\text{ULN}$ (if $\text{ULN} \geq 0.1 \text{ Giga/L}$) and baseline $\leq 0.1 \text{ Giga/L}$ or $\leq \text{ULN}$ (if $\text{ULN} \geq 0.1 \text{ Giga/L}$)	
Eosinophils	$>0.5 \text{ Giga/L}$ or $>\text{ULN}$ (if $\text{ULN} \geq 0.5 \text{ Giga/L}$) and baseline $\leq 0.5 \text{ Giga/L}$ or $\leq \text{ULN}$ (if $\text{ULN} \geq 0.5 \text{ Giga/L}$)	Harrison- Principles of Internal Medicine 17 th Ed., 2008.

Parameter	PCSV	Comments

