Platelets	
< 100 Giga/L or $<$LLN (if LLN≤ 100 Giga/L) and baseline ≥ 100 Giga/L or \geqLLN (if LLN≤ 100 Giga/L)
 
≥ 700 Giga/L or \geqULN (if ULN≥ 700 Giga/L) and baseline < 700 Giga/L or $<$ULN (if ULN≥ 700 Giga/L)
	
International Consensus meeting on drug-induced blood cytopenias, 1991.
 
Two independent criteria

Coagulation Parameters		
INR	> 2.5	

Parameter	PCSV	Comments
PT	>2.5 x ULN	
aPTT	>2.5 x ULN	
Vital signs		
HR	<45 bpm and decrease from baseline \geq 20 bpm \geq 120 bpm and increase from baseline \geq 20 bpm	To be applied for all positions except STANDING
SBP	\leq 95 mmHg and decrease from baseline \geq 20mmHg \geq 160 mmHg and increase from baseline \geq 20 mmHg	To be applied for all positions except STANDING
DBP	\leq 45 mmHg and decrease from baseline \geq 10 mmHg \geq 110 mmHg and increase from baseline \geq 10 mmHg	To be applied for all positions except STANDING

Signature Page for VV-RIM-00160102 v1.0

ESig Approval

2021 23:17:35 GMT+0000

ESig Approval

00

ESig Approval

21 23:47:28 GMT+0000

ESig Approval

00

ESig Approval

00

ESig Approval

2021 00:44:30 GMT+0000

Signature Page for VV-RIM-00160102 v1.0 Approved

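### In the counts of potentially clinically significant values (PCSV), SAP 10.3 cannot flag a low lymphocyte count and has no criterion for SpO2 or temperature

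*SAP*

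**What the plan says.** SAP 5.7 names one place for the thresholds: "Thresholds for Potential Clinically Significant Values (PCSV) in laboratory variables and vital signs are defined in Section" 10.3. SAP 5.7.2 also refers to that appendix and commits to the number and percentage of patients with a PCSV for each clinical laboratory test. Lymphocytes are one of those tests, as part of the differential listed in SAP 4.6.3.

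The lymphocyte row in SAP 10.3 holds a single rule: ">4.0 \text{ Giga/L}$ or $>\text{ULN}$ (if $\text{ULN} \geq 4.0 \text{ Giga/L", with baseline not above the same limit. There is no lower limit. Neutrophils, in the next row, do have low-side limits, including "<0.5 \text{ Giga/L}$ regardless of baseline value or race". White cells and platelets have them too. The comment on the white-cell row reads "To be interpreted only if no differential count available".

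For vital signs, SAP 5.7.3 says: "Vital signs (temperature, pulse, blood pressure, SpO₂, FiO₂, and respiration rate) will be summarized using descriptive statistics". Its next sentence commits to PCSV counts at any time after randomization, without naming parameters. Protocol 11.4.10.2 says the same. The vital-sign block of SAP 10.3 has three rows: heart rate ("<45 bpm and decrease from baseline \geq 20 bpm \geq 120 bpm and increase from baseline \geq 20 bpm"), systolic pressure (its low side is "\leq 95 mmHg and decrease from baseline \geq 20mmHg") and diastolic pressure. The table ends there.

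**The concern.** A PCSV table answers a question that a mean does not: how many patients in each arm crossed a limit that they had not crossed at baseline. For lymphocytes, SAP 10.3 asks this only about rises. A fall also has a claim to attention, because it raises the neutrophil-lymphocyte ratio (NLR). Protocol 9.2.8.2 says of that ratio: "NLR is an inflammatory marker that may serve as an independent risk factor for in-hospital mortality of patients with COVID-19".

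For SpO2 and temperature the question is not asked in either direction, although both are measured before and after the infusion in phases 2 and 3 (Protocol Table 2, footnote 8).

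The gap matters somewhat more here because adverse event collection is narrow. Protocol 10.1.1 limits phases 2 and 3 to SAEs and AESIs, with grade 3 or 4 events recorded in phase 1 only. Non-serious laboratory and vital-sign changes therefore depend largely on the laboratory and vital-sign displays. If limits were chosen after the arms had been compared, the choice would be open to selection.

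**Working it through.** No formula or stated figure is involved. The check compares what is collected, what is to be counted, and what has a criterion.

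| Measure | Collected after dosing | PCSV count promised | Criterion in SAP 10.3 |
|---|---|---|---|
| Lymphocytes | Yes, scheduled differential | Yes, each laboratory test (5.7.2) | High side only |
| Heart rate, blood pressure | Yes | Yes (5.7.3) | Low and high side |
| SpO2 | Yes, pre- and post-dose | Yes, on the wider reading of 5.7.3 | None |
| Temperature | Yes, pre- and post-dose | Yes, on the wider reading of 5.7.3 | None |
| Respiratory rate | Phase 1 only (Protocol 9.2.3.1) | Same | None |
| FiO2 | Only if ventilated; SAP 4.6.4 describes it at baseline | Same | None |

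**Lymphocytes.** Take a fall from 1.5 to 0.3 Giga/L. The only test is whether 0.3 exceeds 4.0 (or the ULN, if that is higher). It does not, so the patient is not counted. The same holds for every low value, so the flagged count of low lymphocytes is zero by construction.

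**Could the white-cell row catch it?** Its comment sets the row aside when a differential is available, and the differential is scheduled. Suppose the comment were ignored and all other cell types stayed constant. The fall of 1.5 − 0.3 = 1.2 Giga/L then brings the total below the 3.0 limit (non-Black patients) only if baseline was below 3.0 + 1.2 = 4.2. The row also requires baseline of at least 3.0. Only patients starting between 3.0 and 4.2 would be flagged. For the 2.0 limit (Black patients) the range is 2.0 to 3.2.

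**Could the general definition fill the gap?** SAP 5.7.2 describes a treatment-emergent PCSV as a value that was normal before treatment and abnormal after it. That could include a value below LLN, but its next sentence refers the reader to SAP 10.3 for the criteria, and the rule there is high-sided.

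**Do other displays give the count?**
- Descriptive statistics (SAP 5) include minimum, Q1, median and Q3. They show how low values went, but not how many patients fell below a limit.
- NLR is summarized descriptively at each visit through day 29. It moves with neutrophils as well as lymphocytes.
- Shift tables would give a count, but SAP 5.7.2 makes them optional.
- SAE and AESI reports depend on the investigator judging that the finding qualifies.

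**What is still blinded?** The 22 December 2020 lock covered patients randomized through 1 December 2020 in phase 1 and in phase 2 cohorts 1, 2 and 3: 60 + 629 + 164 + 35 = 888 of about 2252. Not yet unblinded are 755 + 609 = 1364. In the combined phase 1/2/3 cohort 1 safety set of 60 + 629 + 755 = 1444, there are 689 patients (48%) whose data were already analysed unblinded.

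**The case against.** A reader might infer that low lymphocytes, desaturation or fever could never appear in the safety results. The documents do not support that. The routes listed above remain open. Protocol 10.1.1 also asks for isolated abnormal findings to be reported if they meet the study's criteria or need corrective treatment. Grade ≥2 infusion-related and hypersensitivity reactions are AESIs, which is the natural route for important post-infusion fever or desaturation. Daily oxygen-device status is recorded, and invasive ventilation is in the primary endpoint. The gap is confined to the PCSV counts.

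Three other tempting readings also go too far:
- **That the PCSV tables are the main safety display.** Neither document says so. Nor are visit means the only alternative, since the summaries include the minimum and quartiles.
- **That four of the six vital signs named in SAP 5.7.3 are equal defects.** Respiratory rate is phase 1 only and FiO2 applies to ventilated patients. The clear gaps are SpO2 and temperature.
- **That 93% is the protocol's general SpO2 boundary.** It is the cohort 1 entry limit on low-flow oxygen. Section 7.2 also uses 96% on a non-rebreather mask (cohort 2) and 94% on room air (phase 1 exclusion). SpO2 also depends on the oxygen delivered.

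It can also be argued that the PCSV sentence in SAP 5.7.3 covers only parameters that have criteria. That is a possible reading, but the text does not say so. For laboratory tests SAP 5.7.2 leaves no such room.

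Finally, low lymphocytes are not among the identified or potential risks in Protocol 3.3.2. That limits the priority of the point. It does not explain why the count runs in one direction only.

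**Conclusion.** The point holds for the PCSV counts and no further. As written, SAP 10.3 yields zero patients with low lymphocytes in every arm and cohort, and it gives no rule for counting SpO2 or temperature. No other display commits the sponsor to a per-arm count of affected patients. The zero follows from the rule and says nothing about how many patients had low values, which the documents do not allow one to derive. Primary endpoints, type I error and power are untouched.

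The conclusion assumes that SAP 10.3 is the only source of criteria, as SAP 5.7 states, and that the scheduled differential is usually available. One uncertainty remains about the adverse event route: SAP 5.7 lists grade 3 or 4 events for all phases, whereas SAP 4.6.1 and Protocol 10.1.1 limit them to phase 1. Even if they were collected in all phases, an investigator-reported event would not replace a count based on measured values.

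The omission may be a template effect. SAP 10.3 has rows for uric acid, cholesterol, triglycerides, lipase, amylase and HbA1c, none of which is in the SAP 4.6.3 panel. That is an inference, as the SAP gives no reason.

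**What to change.** 1. **Lymphocytes.** In SAP 10.3 add a low-side criterion in the value-plus-baseline form of the other rows: below LLN, with baseline at or above LLN. A more severe level could be added from NCI-CTCAE v5.0, which SAP 4.6.1 already uses for grading; its limits are not given in the documents. Read the row against placebo, on the assumption that the disease itself lowers counts in both arms.
2. **SpO2 and temperature.** Reconcile SAP 5.7.3 with 10.3. Either add criteria chosen by the sponsor before the final unblinding, with SpO2 read alongside the oxygen delivered, or state that no PCSV will be reported for these two measures.
3. **FiO2 and respiratory rate.** Limit the PCSV sentence in SAP 5.7.3 so that it does not cover them.
4. **Record the change.** SAP 1.2.4 says that nothing departs from the protocol's statistical section, and Protocol 11.4.10.2 carries the same vital-sign wording. Any narrowing should be noted there. State also that phase 1/2 cohort 1 and cohorts 2 and 3 were analysed unblinded at the December 2020 lock, so the new criteria are fully prespecified only for phase 3 cohort 1 and phase 2 cohort 1A.

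The cost is a few table rows and one or two sentences, using data already collected. The drawback is that a low-lymphocyte row may flag many patients in all arms, so only the comparison with placebo will be informative.
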